13.3 Laboratory Test Abnormalities

All laboratory test results captured as part of the study should be recorded following institutional procedures. Test results that constitute SAEs should be documented and reported to BMS as such.

The following laboratory abnormalities should be documented and reported appropriately:

- any laboratory test result that is clinically significant or meets the definition of an SAE
- any laboratory abnormality that required the participant to have study drug discontinued or interrupted
- any laboratory abnormality that required the subject to receive specific corrective therapy.

It is expected that wherever possible, the clinical rather than laboratory term would be used by the reporting investigator (e.g., anemia versus low hemoglobin value).

Pregnancy

If, following initiation of the investigational product, it is subsequently discovered that a study participant is pregnant or may have been pregnant at the time of investigational product exposure, including during at least 5 half-lives after product administration, the investigational product will be permanently discontinued in an appropriate manner (e.g., dose tapering if necessary for participant).

The Core Medical Monitor must immediately notify DCRI Safety Surveillance of the pregnancy via the BMS Pregnancy Surveillance Form in accordance with SAE reporting procedures.

DCRI Safety Surveillance will perform due diligence follow-up using the BMS Pregnancy Form, which the Core Medical Monitor must complete.

Protocol-required procedures for study discontinuation and follow-up must be performed on the participant.

Follow-up information regarding the course of the pregnancy, including perinatal and neonatal outcome and, where applicable, offspring information must be reported on the BMS Pregnancy Surveillance Form if known within the study participation period. If pregnancy outcome is not known at the time of the participant's last visit of the study, BMS will follow up regarding pregnancy and neonatal outcome. A BMS Pregnancy Surveillance Form may be provided upon request. Any associated AE or SAE should be reported with the EDC.

13.4 Other Safety Considerations

Any significant worsening noted during interim or final physical examinations, electrocardiograms, X-rays, and any other potential safety assessments, whether or not these procedures are required by the protocol, should also be recorded as a non-serious or serious AE, as appropriate, and reported accordingly.

Appendix 4. Biospecimens

Biospecimens will be collected at two time points during the study, at the time of enrollment, and following completion of the antithrombotic therapy being studied (shortly after Day 30 for Stage 1). Samples that would be collected for the biorepository would collect citrated plasma (2 tubes), serum, and a sample for genomic DNA or dried blood spot samples.

At sites capable of sample collection and processing, additional samples sent by the site teams may include: Pax gene DNA; Pax gene RNA; Platelets; and Cryopreserved PBMS.

Appendix 5. Addition of New Key Secondary and Exploratory Outcomes

A5.1 Rationale for new Secondary and Exploratory Outcomes

Health-related quality of life data has been collected on participants in ACTIV 4c by use of the EuroQol 5 Dimension 5 Level (EQ-5D-5L) survey, administered at three timepoints following randomization into the study: Day 2 (within the first few days of starting study drug), Day 30 (time of completion of study drug), and Day 90 (60 days after completion of study drug). The EQ-5D survey consists of five questions that cover the following domains: mobility, self-care, usual activities, pain/discomfort, and anxiety/depression. The response to each question is collected as a 5-level ordinal scale, spanning scores of 1 (no problems, or best outcome), 2 (slight problems), 3 (moderate problems), 4 (severe problems) and 5 (extreme problems, or worst outcome). The rationale for collecting these quality of life data was driven by early reports describing a significant subset of patients with COVID-19 who had a prolonged course with persistent symptoms of fatigue, dyspnea, and other problems, lasting for months and longer after the acute illness.

An analysis of the EQ-5D data was not included in the Master Protocol, since study leadership had not anticipated that anticoagulant therapy would have a significant impact on quality of life. A post-hoc analysis of EQ-5D data collected in ACTIV 4a, however, comparing prophylactic-dose with therapeutic-dose anticoagulation in hospitalized patients with COVID-19 in the non-ICU setting, observed that patients randomized to therapeutic anticoagulation had less moderate-to-extreme impairment scores in four of the five EQ-5D domains at 90 days after hospital discharge. This difference was statistically significant in the self-care domain, with an improvement from 8.4% to 2.9% of participants having moderate-to-extreme impairment scores with therapeutic anticoagulation, for an odds ratio (adjusted for age, co-morbidities and pre-hospitalization status) of 0.26 (95% CI, 0.08-0.83) and a p-value of 0.016 ([name] and [name], personal communication). This preliminary observation that anticoagulant therapy could impact quality of life in patients with COVID-19 resulted in the decision by the ACTIV 4c leadership team to include an analysis of the collected EQ-5D data in two new secondary objectives and one new exploratory objective.

A5.2 New Secondary Objectives

Secondary Objective 1: To compare the effects of treatment at 30 days after randomization for the composite endpoint of QOL and mortality.

Secondary Objective 2: To compare the effects of treatment at 90 days after randomization for the composite endpoint of QOL and mortality.

The existing three secondary objectives in the Master Protocol will now become Secondary Objectives 3, 4, and 5

A5.3 New Exploratory Objective

Exploratory Objective 3: To compare the effects of treatment beginning at the time of discharge from the hospital with either Arm A or Arm B on the individual domains of EQ5D and the EQ5D visual analog scale for 30 and 90 days after randomization.

The existing two exploratory objectives in the Master Protocol will remain as Exploratory Objectives 1 and 2.

A5.4 New Key Secondary Endpoints

The two new key secondary endpoints are:

1. The composite endpoint of EQ5D index score and mortality at day 30 following randomization

Version:5, Date:20APR2022

2. The composite endpoint of EQ5D index score and mortality at day 90 following randomization

The existing four key secondary endpoints in the Master Protocol will now become key secondary endpoints 3 through 6

A5.5 Secondary and Exploratory Endpoints Analyses

Six secondary outcomes are of interest in this trial. We will use a fallback method to control for type I error. Statistical methods for testing the QOL&M30 and QOL&M90 endpoints will be based on a proportional odds model. The covariates in the model will include the participant's age (restricted cubic spline with 3 knots), sex, D-dimer (normal or abnormal), BMI (restricted cubic spline with 3 knots), antiplatelet usage (yes/no - at enrollment), WHO severity score (<five vs. \geq five), and the randomized treatment. The results of these models will be summarized using an odds ratio and associated 95% confidence interval.

Secondary analyses of the QOL&M30 and QOL&M90 endpoints will use a multiple imputation approach. 20 datasets will be imputed using predictive mean matching and the above covariates plus the Day 2 and Day 90 EQ5D index scores. The model estimates will be combined using Rubin's rules to obtain the estimated odds ratio and 95% confidence interval.

More specifically, these secondary outcomes will only be formally tested if the primary hypothesis was rejected at level alpha=0.05. If the study stops without the CE30 test statistic crossing the 'efficacy boundary' or 'futility boundary' (i.e. not enough primary endpoint events), the key secondary endpoints will be evaluated and summarized using point estimates and associated 95% confidence intervals (without p-values).

The ordering of the secondary endpoints is as follows:

- 1) Composite endpoint of mortality and EQ5D index at Day 30 (QOL&M30)
- 2) Composite endpoint of mortality and EQ5D index at Day 90 (QOL&M90)
- 3) Primary endpoint at 45 days (CE45)
- 4) Primary endpoint at 90 days (CE90)
- 5) Venous events at 30 days (CEVTE30)
- 6) Arterial events at 30 days (CEATE30)

Using a fallback method the 0.05 type I error rate would be split as follows – 0.025, 0.005, 0.005, 0.005, 0.005, and 0.005. If QOL&M30 was statistically significant then QOL&M90 would be tested at $0.03 = 0.025 + 0.005$. On the other hand, if QOL&M30 was NOT statistically significant then QOL&M90 would be tested at 0.005. The process would continue until all 6 secondary endpoints were tested. If the study does not accumulate enough CE30 events, it is expected that there would be limited information for secondary endpoints 3-6.

Statistical methods for testing the secondary endpoints 3-6 listed above will follow exactly the same procedures used for the primary endpoint described in Section 4.2 in the Master Protocol.

Additional details concerning the analysis of the new key secondary and exploratory endpoints are included in the Statistical Analysis Plan.

Appendix 6. Protocol Summary of Changes**Summary of Changes protocol version 4.0 to 5.0**

| Protocol Section | Section Name | | |
|------------------|--|-----------|------------------------|
| Title Page | N/A | Previous | Version 4.0, 20OCT2021 |
| | | Update | Version 5.0, 20APR2022 |
| | | Rationale | Update version |
| A5 | Addition of New Key Secondary and Exploratory Outcomes | Previous | NA |
| | | Update | All Appendix 5 is new. |

## LIST OF ABBREVIATIONS

ACTIV	Accelerating COVID-19 Therapeutic Interventions and Vaccines
CRNMB	Clinically Relevant non-Major Bleeding
CE	Composite Endpoint
CEx	Composite Endpoint at Day x
CEATE30	Composite Arterial Endpoint at Day 30
CEVTE30	Composite Venus Endpoint at Day 30
CI	Confidence Interval
COVID-19	Coronavirus disease 2019
DSMB	Data and Safety Monitoring Board
DVT	Deep Venous Thrombosis
FDA	Food and Drug Administration
HIPAA	Health Insurance Portability and Accountability Act
ICF	Informed Consent Form
IRB	Institutional Review Board
ICU	Intensive Care Unit
ISTH	International Society on Thrombosis and Haemostasis
ITT	Intent to Treat
LAR	Legally Authorized Representative
LMWH	Low Molecular Weight Heparin
miITT	Modified ITT
NIH	National Institutes of Health
PE	Pulmonary Embolism
PI	Principal Investigator
QOL&M30	Composite endpoint of EQ5D and Mortality at Day 30
QOL&M90	Composite endpoint of EQ5D and Mortality at Day 90
SAE	Serious Adverse Event
SARS-CoV2	Severe Acute Respiratory Syndrome Coronavirus 2
SAP	Statistical Analysis Plan
VTE	Venous thromboembolism
WHO	World Health Organization

## 1.0 STUDY AND DOCUMENT OVERVIEW

ACTIV-4C study is an adaptive, prospective, randomized trial designed to compare the effectiveness and safety of antithrombotic therapy with no antithrombotic therapy after hospitalization for 48 hours or longer for Coronavirus disease 2019 (COVID-19) resulting from severe acute respiratory syndrome coronavirus 2 (SARS-CoV-2). For Stage 1 of this study, participants will be randomized to either prophylactic anticoagulation or placebo for 30 days, and then followed for an additional 60 days after the completion of treatment (total duration of follow-up, approximately 90 days).

This document describes the planned statistical analyses that will be conducted during (interim) and at the completion of stage 1 of the study. Once the initial unblinded data review has occurred, only the blinded statistics team members will be allowed to modify the SAP (see **Appendix 1** for the list of blinded and unblinded statisticians). The initial interim review is expected to occur when 20% of the information fraction is accumulated.

The study population corresponds to adults at least 18 years of age with COVID-19 who are hospitalized for 48 hours or longer and who are ready for discharge from the hospital. Patients both with and without intensive care unit (ICU) stay will be included in the study population. Key exclusion criteria are a clinical requirement for anticoagulant therapy (therapeutic dose or prophylactic dose), contraindication to anticoagulant therapy, and anticipated life expectancy < 90 days.

Enrollment into this first stage of the ACTIV-4C study began in February 2021.

The study period is 90 days, with follow-up assessments on days 2, 10, 20, 30, 45, and 90 days from randomization. The initial follow-up encounter, which will be conducted by the Call Center via the participant's preferred method (electronic or phone call), will occur within 2 days following discharge from the hospital, to confirm study medication adherence and perform an initial assessment of outcomes. Subsequent encounters, which will also be conducted by the Call Center electronically or by phone, will occur at 10, 20, and 30 days after enrollment. With each encounter, assessments of medication adherence and outcomes will be performed. Two additional encounters will occur after completion of the primary outcome, at 45 and 90 days after enrollment, to determine if there is an increased risk for thromboembolic complications following hospital discharge that extends for a longer period than 30 days and to facilitate/confirm collection of the 2nd set of biorepository specimens.

This first stage of the ACTIV-4C trial uses a group-sequential design where interim analyses are planned to assess the efficacy and futility of the treatments with the potential for early stopping. Proper statistical approaches are used to control type I error at the interim and final analyses. Safety monitoring will be performed throughout the trial and will be periodically reported by the Data and Safety Monitoring Board (DSMB) established for ACTIV-4C which will have oversight responsibility for the study.

## 2.0 STUDY OBJECTIVES

### Primary Objective:

- The primary objective of this first stage of the ACTIV-4C trial is to compare the effects of treatment beginning at the time of discharge from the hospital with either (i) anticoagulation at a prophylactic dose, or (ii) placebo (no anticoagulation) for up to 30 days after randomization on the composite endpoint of venous and arterial thromboembolic outcomes, and all-cause mortality.

**Secondary Objectives:**

- Secondary Objective 1: To compare the effects of treatment at 30 days after randomization for the composite endpoint of QOL and mortality.
- Secondary Objective 2: To compare the effects of treatment at 90 days after randomization for the composite endpoint of QOL and mortality.
- Secondary Objective 3: To compare the effects of treatment beginning at the time of discharge from the hospital with either Arm A or Arm B on the incidence of the composite outcome at 45 days and at 90 days after randomization.
- Secondary Objective 4: To compare the effects of treatment beginning at the time of discharge from the hospital with either Arm A or Arm B on the incidence of new, symptomatic VTE (inclusive of Deep Venous Thrombosis (DVT), PE, or other venous thrombosis) for up to 30 days after randomization.
- Secondary Objective 5: To compare the effects of treatment beginning at the time of discharge from the hospital with either Arm A or Arm B on the incidence of new, symptomatic ATE (inclusive of ischemic stroke, MI, or peripheral arterial thromboembolism) for up to 30 days after randomization.

**Exploratory Objectives:**

- Exploratory Objective 1: To compare the effects of treatment beginning at the time of discharge from the hospital with either Arm A or Arm B on the incidence of all-cause rehospitalization for up to 90 days after randomization.
- Exploratory Objective 2: To compare the effects of treatment beginning at the time of discharge from the hospital with either Arm A or Arm B on the incidence of all-cause mortality for up to 30 days after randomization.
- Exploratory Objective 3: To compare the effects of treatment beginning at the time of discharge from the hospital with either Arm A or Arm B on the individual domains of EQ5D and the EQ5D visual analog scale for 30 and 90 days after randomization.

### 3.0 STUDY ENDPOINTS

#### 3.1 PRIMARY STUDY ENDPOINTS

At approximately day 30 from randomization, a binary composite endpoint of venous and arterial thrombotic complications—including new, symptomatic proximal, or distal DVT of the upper or lower extremities, PE, and new thrombosis of other veins (including cerebral sinus and splanchnic veins), ischemic stroke, myocardial infarction, other arterial thromboembolism (e.g., mesenteric or acute limb ischemia), and all-cause mortality will be the primary study endpoint.

#### 3.2 KEY SECONDARY AND EXPLORATORY ENDPOINTS

Key secondary endpoints include the following.

1. The composite endpoint of EQ5D index score and mortality at day 30 following randomization
2. The composite endpoint of EQ5D index score and mortality at day 90 following randomization
3. The composite endpoint for the primary outcome at day 45 following randomization
4. The composite endpoint for the primary outcome at day 90 following randomization
5. Composite endpoint of venous thromboembolic events, including symptomatic DVT of the upper or lower extremities, symptomatic and/or clinically relevant PE, and other symptomatic venous thrombosis, including cerebral sinus and splanchnic vein thrombosis at day 30
6. Composite endpoint of arterial thromboembolic events, including symptomatic ischemic stroke, myocardial infarction, and other symptomatic arterial thromboembolic events at day 30

Secondary endpoints will be formally tested using a fallback approach (see Section 4.3) only if the primary endpoint was statistically significant at the two-sided 5% level.

Exploratory endpoints include the following.

1. All-cause mortality at day 30 following discharge from the hospital
2. All-cause re-hospitalization at day 90 following discharge from the hospital

Table 1. Summary of important questions of interest and related estimands

Row	Question of Interest	Objective Description / Study Population	Endpoint	Intercurrent Events/Strategy to handle	Population Summary Estimands
1	Does Apixaban reduce the rate of venous and arterial thromboembolic outcomes, and all-cause mortality during 30 days after discharge?	Primary Objective of the Study / All Randomized Participants	Composite endpoint (CE) of venous and arterial thrombotic complications—including new, symptomatic proximal, or distal DVT of the upper or lower extremities, PE, and new thrombosis of other veins (including cerebral sinus and	The only intercurrent event will be patient drop-out. The drop-out is expected to be less than 5% and un-related to treatment and their data up to the time of drop-out will be	The difference in the proportion of CE between the Apixaban arm and the placebo arm. A negative value will favor the

			splanchnic veins), ischemic stroke, myocardial infarction, other arterial thromboembolism (e.g., mesenteric or acute limb ischemia), and all-cause mortality by day 30	used in the event determination*	Apixaban arm.
2	Does Apixaban improve the composite of QOL and mortality at 30 days after discharge?	Key Secondary Objective of the Study / All Randomized Participants	Composite endpoint of mortality and EQ5D index at Day 30. All mortality events will be considered worse than any possible EQ5D response [QOL&M30]	The expected rate of missing data for the EQ5D endpoint is expected to be approximately 20%. The odds ratio will be estimated using maximum likelihood methods which yield valid estimators under the MAR (or MCAR) assumptions.	The odds ratio from a proportional odds model with the EQ5D index and mortality endpoint as the response variable. Values greater than 1.0 will favor the Apixaban arm.
3	Does Apixaban improve the composite of QOL and mortality at 90 days after discharge?	Key Secondary Objective of the Study / All Randomized Participants	Composite endpoint of mortality and EQ5D index at Day 90. All mortality events will be considered worse than any possible EQ5D response [QOL&M90]	The expected rate of missing data for the EQ5D endpoint is expected to be approximately 20%. The odds ratio will be estimated using maximum likelihood methods which yield valid estimators under the MAR (or MCAR) assumptions.	The odds ratio from a proportional odds model with the EQ5D index and mortality endpoint as the response variable. Values greater than 1.0 will favor the Apixaban arm.
4	Does Apixaban reduce the rate of venous	Key Secondary Objective of	Composite endpoint of venous thromboembolic	Inter-current events will be death and	The difference in the

	thromboembolic outcomes during 30 days after discharge?	the Study / All Randomized Participants	events, including symptomatic DVT of the upper or lower extremities, symptomatic and/or clinically relevant PE, and other symptomatic venous thrombosis, including cerebral sinus and splanchnic vein thrombosis at day 30 [CEVTE30]	patient drop-out. Patients who died without an intercurrent event will be censored. The drop-out is expected to be less than 5% and un-related to treatment and their data up to the time of drop-out will be used in the event determination*	proportion of CEVTE30 between the Apixaban arm and the placebo arm. A negative value will favor the Apixaban arm.
5	Does Apixaban reduce the rate of arterial thromboembolic outcomes during 30 days after discharge?	Key Secondary Objective of the Study / All Randomized Participants	Composite endpoint of arterial thromboembolic events, including symptomatic ischemic stroke, myocardial infarction, and other symptomatic arterial thromboembolic events at day 30 [CEATE30]	Inter-current events will be death and patient drop-out. Patients who died without an intercurrent event will be censored. The drop-out is expected to be less than 5% and un-related to treatment and a complete-case analysis will be employed*	The difference in the proportion of CEATE30 between the Apixaban arm and the placebo arm. A negative value will favor the Apixaban arm.
6	Does Apixaban reduce the rate of venous and arterial thromboembolic outcomes, and all-cause mortality during 45 days after discharge?	Key Secondary Objective of the Study / All Randomized Participants	Composite endpoint of venous and arterial thrombotic complications—including new, symptomatic proximal, or distal DVT of the upper or lower extremities, PE, and new thrombosis of	The only inter-current event will be patient drop-out. The drop-out is expected to be less than 5% and un-related to treatment and their data up to	The difference in the proportion of CE45 between the Apixaban arm and the placebo arm. A negative

			other veins (including cerebral sinus and splanchnic veins), ischemic stroke, myocardial infarction, other arterial thromboembolism (e.g., mesenteric or acute limb ischemia), and all-cause mortality by day 45 [CE45]	the time of drop-out will be used in the event determination*	value will favor the Apixaban arm.
7	Does Apixaban reduce the rate of venous and arterial thromboembolic outcomes, and all-cause mortality during 90 days after discharge?	Key Secondary Objective of the Study / All Randomized Participants	Composite endpoint of venous and arterial thrombotic complications—including new, symptomatic proximal, or distal DVT of the upper or lower extremities, PE, and new thrombosis of other veins (including cerebral sinus and splanchnic veins), ischemic stroke, myocardial infarction, other arterial thromboembolism (e.g., mesenteric or acute limb ischemia), and all-cause mortality by day 90 [CE90]	The only inter-current event will be patient drop-out. The drop-out is expected to be less than 5% and un-related to treatment and their data up to the time of drop-out will be used in the event determination*	The difference in the proportion of CE90 between the Apixaban arm and the placebo arm. A negative value will favor the Apixaban arm.

\*See the sensitivity analysis (Section 4.2)

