5.6 Participant Withdrawal or Termination

5.6.1 Reasons for Withdrawal or Termination

Study participants are free to withdraw from participation in the study at any time upon written request. The site PI will notify the Clinical Coordinating Center of all withdrawals from the study. Study participants who withdraw consent will not have additional information collected after they withdraw from the study.

A site investigator may discontinue study drug for a study participant on the basis of either:

- Any clinical adverse event, laboratory abnormality, or other medical condition or situation occurs such that continued study drug treatment would not be in the best interest of the patient.
- The participant meets an exclusion criterion, either newly developed or not previously recognized (e.g., new thrombocytopenia, renal insufficiency), that precludes further study medication continuation.

Study participants may choose to withdraw from participation in the study at any time.

As noted above, study participants who discontinue taking the study drug prior to completing 30 days of therapy will continue to be followed as study participants, unless they also request to be withdrawn from the study.

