6.3 Concomitant Medications, Treatments, and Procedures

Concomitant medications taken during study participation will be recorded on the case report forms (CRFs). Concomitant medications to be recorded are:

1. Antiplatelet therapies (e.g., aspirin, clopidogrel)
2. Anticoagulant medications that may be prescribed to the participant after randomization and discharge from the hospital (e.g., a new prescription introduced by an outpatient provider, without notification of the study team, in response to a clinical concern about thrombosis risk or symptoms)
3. Other therapies that may impact arm-specific appendices

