7.5 Tabulation of Individual Response Data

The composite outcome evaluated will be tabulated and broken down by component (e.g., death, pulmonary embolus, symptomatic DVT, myocardial infarction, etc.). Note that all clinical endpoint events that occur during the 30-day treatment period will be collected regardless of whether a patient discontinues therapy or experiences an initial clinical event. As a result, some participants may experience more than one component of the primary endpoint. Event rates and relative risks and the absolute risk difference between treatment groups will be calculated with their confidence intervals for each of the defined secondary endpoints.

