#### 4.4 SAFETY ANALYSES

The rates of safety outcomes listed in section 3.0.3 (e.g., ISTH major bleeding and the rate of ISTH CRNMB) during the 30-day treatment period and during the additional 60-day safety follow-up period between the two arms will be compared. The proportion of patients in each assigned treatment group who experience each safety event, the relative risk, and the absolute risk difference will be calculated from the observed data, and confidence intervals will be calculated. Analyses of the bleeding outcomes that occur during the full 90-day follow-up period (i.e., 30-day treatment period plus the 60-day safety follow-up) will also be conducted as part of the trial safety analyses. This analysis will be done for mITT population only (participants who had at least one dose of the drugs).

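### Bleeding is compared only by assigned arm over fixed windows, with no on-treatment analysis and no report of open-label anticoagulation, two gaps that the estimand table also passes over

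*SAP*

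**What the plan says.** **Estimands.** The estimand table in SAP 3.2 says of the primary composite (CE30): "The only intercurrent event will be patient drop-out". The rows for the composite at 45 and 90 days say the same. The venous and arterial rows add one item: "Inter-current events will be death and patient drop-out". The two EQ5D rows discuss missing data only. No row names stopping of study drug or a new anticoagulant, and no row covers bleeding.

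**What the protocol foresees.** Protocol 6.3 has the case report forms record "Anticoagulant medications that may be prescribed to the participant after randomization and discharge from the hospital". Protocol 5.6.1 lets a site investigator stop study drug for an adverse event or a newly met exclusion criterion, and adds that "study participants who discontinue taking the study drug prior to completing 30 days of therapy will continue to be followed as study participants". Those who withdraw from the trial altogether are the exception. Protocol 7.5 says that "all clinical endpoint events that occur during the 30-day treatment period will be collected regardless of whether a patient discontinues therapy".

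**Bleeding analysis.** Under SAP 4.4, the rates of major and clinically relevant non-major bleeding "during the 30-day treatment period and during the additional 60-day safety follow-up period between the two arms will be compared", and the full 90 days are analysed as well. Proportions are taken by assigned group in the mITT set, meaning participants with at least one dose.

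**What is reported on adherence.** SAP 3.11 summarises compliance and the timing and reasons of early discontinuation by arm. SAP Appendix 3, part C, tabulates missed pills, interruptions and permanent stops by arm.

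**The concern.** A table with a column for intercurrent events and their handling should list the events that the protocol itself expects and records. Two are absent.

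For efficacy, counting every event by assigned arm is a legitimate choice, and where crossover weakens the contrast it works against the sponsor. For bleeding the direction of caution reverses: anything that draws the arms together makes the drug look safer. A bleed on Day 25 in a participant who stopped apixaban on Day 3 counts as an apixaban bleed, although by then the risk is close to that of no treatment. A bleed in a placebo participant given an outside anticoagulant counts as a placebo bleed. Restricting to mITT removes only those who never started.

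The two provisions can act together. An existing indication for anticoagulation is an exclusion criterion (Protocol 5.2), so a participant with a new thrombosis may meet it, stop study drug and start an outside anticoagulant. If apixaban works, that happens more often on placebo. The stated objective is the most effective and safe strategy, so the bleeding contrast carries weight.

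**Working it through.** **1. The plan's own sample size.** Inputs from Protocol 7.2: composite rate 4.0% on placebo, risk ratio 0.65 (so 2.6%), two-sided 0.05, 80% power, pooled Z-test.

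n per arm = [1.96·√(2·0.033·0.967) + 0.84·√(0.026·0.974 + 0.040·0.960)]² / 0.014² ≈ 2,555

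This is within 1% of the stated 2,530, and 2,530/0.95 ≈ 2,663, the stated figure of about 2,660. The only allowance is 5% for missing outcomes; there is none for stopping or crossover.

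**2. Model for bleeding.** Let *a* be the bleeding risk on drug and *p* the risk off drug. Let *s* be the share of apixaban-arm risk time off drug, and *c* the share of placebo-arm risk time on an open-label anticoagulant with the same bleeding risk as apixaban.

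- Apixaban arm: a − s(a − p)
- Placebo arm: p + c(a − p)
- Difference: (1 − s − c)(a − p)

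The documents give neither *s* nor *c*; both are assumptions, shown over a range.

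**3. Major bleeding, apixaban trial in Protocol Table 2** (a = 0.47%, p = 0.19%). Its comparator was enoxaparin for 6–14 days, not placebo, so 0.19% only stands in for an untreated rate. Expected excess bleeds and fixed-sample power (two-sided 0.05) use 2,530 per arm.

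| s, c | Arms | Difference (points) | Kept | RR | Excess bleeds | Power |
|---|---|---|---|---|---|---|
| 0, 0 | 0.470% v 0.190% | 0.280 | 100% | 2.47 | 7.1 | 41% |
| 5%, 2% | 0.456% v 0.196% | 0.260 | 93% | 2.33 | 6.6 | 37% |
| 10%, 5% | 0.442% v 0.204% | 0.238 | 85% | 2.17 | 6.0 | 32% |
| 20%, 10% | 0.414% v 0.218% | 0.196 | 70% | 1.90 | 5.0 | 24% |

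**4. Other rates in Protocol Table 2, same scenarios.** With 1.1% v 0.4% major bleeding (MAGELLAN, placebo comparator), RR goes from 2.75 to 2.57, 2.37 and 2.04, and power from 82% to 77%, 70% and 54%. With 4.1% v 1.7% clinically relevant bleeding in the same trial, the difference goes from 2.40 points to 2.23, 2.04 and 1.68, and power stays at 95% or more. Rare major bleeding is the sensitive case.

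**5. How far thrombosis alone could drive crossover.** The planned placebo composite rate is 4%, deaths included. If every event were a non-fatal thrombosis, spread evenly over 30 days and then anticoagulated, open-label use would cover about 4% × ½ = 2% of placebo time, against 2.6% × ½ = 1.3% on apixaban. Values of *c* of 5–10% therefore also need precautionary prescribing by outside providers.

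**6. Direction.** If a share *d* of apixaban-arm time is on an open-label anticoagulant with bleeding risk *b*, the difference becomes (1 − s − c)(a − p) + d(b − a). It exceeds the undiluted value when d(b − a) > (s + c)(a − p). At s = 10% and c = 5% the right side is 0.15 × 0.28 = 0.042 points; with d = 5%, *b* would have to exceed *a* by 0.042/0.05 = 0.84 points. Dilution is therefore possible, not assured.

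**The case against.** The strongest reply is that the trial has already chosen treatment policy in substance. All randomised participants are analysed, follow-up continues after study drug stops, and events count whether or not the participant is on drug. Missing outcomes from drop-out have a two-dimensional tipping-point analysis in SAP 4.2. This stands: for efficacy, amending Table 1 changes no result.

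A reader might also infer that the bleeding comparison is diluted and that nothing would reveal it. The documents do not support either half. Stopping, interruption, missed pills and reasons are reported by arm. The safety listings in SAP 3.7.1 include treatment adjustment, and the SAE listings in Appendix 3 give the study-medication day. Protocol 6.3 says only that outside anticoagulants may be prescribed, and no rate is given. A stop prompted by a bleed does not remove that first bleed from the count.

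The absolute numbers are also small. At the apixaban-trial rates the excess falls by between half a bleed and about two bleeds at 2,530 per arm, and power for major bleeding is only 41% with no crossover at all.

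What remains is narrower. A count of stops does not give the bleeding difference while on drug, and the listings describe single cases. The anticoagulant list in SAP Appendix 3 is a baseline list; use after randomisation enters no table or analysis. Uncertainty about size and direction is a reason to tabulate it.

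**Conclusion.** The concern holds in limited form, as an inexpensive improvement to the safety analysis. The estimand table omits two events that the protocol foresees; for efficacy that is a matter of naming. SAP 4.4 offers one view of bleeding, by assigned arm over fixed windows, and that view can understate the bleeding cost of taking the drug.

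Under assumed values from 5% off drug with 2% crossover up to 20% with 10%, the major-bleeding difference keeps 93% down to 70% of its value. This rests on assumed rates, on equal bleeding risk for open-label drug and apixaban, on no open-label use in the apixaban arm, and on a comparator rate from short-course enoxaparin. The true figure could be smaller, or the effect could run the other way.

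Two stronger readings should be set aside. The primary test is not invalidated. Nor should the planned risk ratio of 0.65 be discounted for crossover: Protocol 7.2 gives it as the planning effect for an intention-to-treat comparison, so a further discount could count the dilution twice. The DSMB review trigger in Protocol A3.3 is not at issue either: a 5% excess, read as an absolute difference, lies above even the undiluted 2.4 points.

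**What to change.** Keep the primary ITT test and the mITT bleeding analysis as they are. Then:

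1. In SAP 4.4, add a prespecified supplementary on-treatment bleeding analysis. It runs from first dose to last dose plus a stated fixed window and ends at any open-label anticoagulant start. Tabulate later bleeds separately by arm.
2. Tabulate post-randomisation open-label anticoagulation by arm and, where recorded, by whether it began before or after a primary event.
3. In the SAP 3.2 estimand table, name early stopping and open-label anticoagulation as intercurrent events under treatment policy, for consistency with the analysis already planned.

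An on-treatment version of CE30 is not needed. Participants who deteriorate may stop drug, and with all-cause death in the composite that would bias the result.

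**Cost.** SAP wording and programming; no alpha and no change to the primary test. Protocol 6.3 has the anticoagulants recorded but does not say that start dates or reasons are captured, so confirm this first. Some prescriptions may be missed, because the same section anticipates prescribing without notice to the study team. SAP 1.0 lets the blinded statisticians amend the plan, and the window should be fixed before unblinding.

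**Downside.** The on-treatment comparison is not protected by randomisation, and ending follow-up at an open-label start may be informative, since that start can follow a thrombosis. It must be labelled supplementary.
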